### Secondary Outcomes

1) Other scales on the ASI constitute some of our secondary outcomes, including medical, family/social and psychological. 2) Days worked over the assessment time period is a measure is taken from Gerstein et al. (1994) and is a simple count of number of days worked over the follow-up time point. We will also assess days involved in vocational training, GED or other schooling. 3) Housing stability is taken from our previous study of SLHs depicting the usual housing situation over the past 6 months as well as the number of day homeless or residence in a shelter. We will have additional questions that assess whether there are any requirements to live in the home, such as abstinence from alcohol and drug use, compliance with a curfew, attendance at 12-step meetings, or involvement in counseling.

### Mediators and Moderators of Outcome

1) A short form measuring social support will ask about support from people close to the respondent. 2) We will ask three questions to assess the extent to which individuals in their social network are heavy alcohol and drug users. 3) The Alcoholics Anonymous

Affiliation Scale (AAS) is a nine-item scale that measures the strength of an individual's affiliation with AA and other 12-step groups (Humphreys, Kaskutas & Weisner, 1998). 4) Services Received is a measure from our current study of SLHs that assesses the extent to which participants are involved in a variety of services (e.g., substance abuse, mental health, healthcare, legal and job training) (Hser et al., 1999). 5) Supportive confrontation will be assessed using the Alcohol and Drug Confrontation Scale (ADCS) developed by [name] et al (2006; [name] & Greenfield, 2006). Confrontation is defined as warnings individuals receive about potential consequences of alcohol or drug use from family, friends, peers and professionals. 6) Retention will be assessed as number of continuous days of residence after admission. 7) We will ask a set of questions about the effects of traumatic life events using a PTSD checklist. We will ask about their history of physical and sexual abuse using questions adapted from the National Alcohol Study and the WHO women and violence study. 8) The Alcohol and Drug Consequences Questionnaire (Cunningham, et al., 1997) will be used to assess motivation for change. Two scales assess the consequences and benefits of changing substance use. Consistent with previous studies of SLHs ([name] & Greenfield, 2006) we will also use these items to assess motivation to maintain abstinence.

#### Biological Measures

1) Urine screens will be administered to corroborate self-report of drug use. Self-reported use will be the default measure unless a report of no use is falsified by a positive urine screen (Leiderman & Bigelow, 1999).

#### Qualitative Interviews

Qualitative interviews will be conducted with approximately 13-15 participants in each study condition (N=28). See the subheading above entitled "Qualitative Interviews" for a description of the items used.

#### House Environment

The Social Model Philosophy Scale (SMPS) (Kaskutas et al, 1998) will be used to measure the physical and social environment at each house. The SMPS assesses the physical environment, house manager roles, authority base, governance, view of recovery, and orientation toward the surrounding community. The scale will be assessed at each house that has signed a letter agreement and where we enrolled study participants. The respondent will be compensated with a \$5 gift card for this scale that will take approximately 15 minutes to complete. The SMPS is scored along six domains and has an overall internal reliability of 0.92. Should differences exist across the 30 houses used in the proposed study, we will investigate whether those differences are associated with outcome.

### **E. Assessment of Benefits**

Direct benefits include \$30 for participation in the baseline interview and \$50 for participation in the 6- and 12-month follow up interviews as well as a \$5 gift card for confirming/updating their locator information at the 3-month interim contact and a \$10 gift card for confirming/updating their locator information at the 9-month interim contact. The 28 individuals taking part in the qualitative component will be compensated \$20. Participants in the 2 study conditions may benefit through residing in a sober living residence that supports abstinence from alcohol and drugs. The MICM intervention condition may also benefit through accessing community supports with the assistance of the therapist. The comparison condition might benefit through provision

of alcohol and drug free housing and acquisition of a list of referral resources that might be helpful to them. All individuals in the study may benefit by the self-reflection required of the research questions.

#### **F. Assessment of Risks**

This study is a clinical trial. Our sample targets 330 individuals who are on probation or parole and are entering a sober living house in Los Angeles County. Risks that the research participants may undergo are expected to be minimal. They may feel uncomfortable or embarrassed by some questions. For example, they may feel discomfort about providing information about their substance use patterns, illegal behaviors, and psychiatric symptoms. However, the questions asked of them are typical counseling questions that are often asked as part of any treatment or recovery program. Participants may also be embarrassed by a positive urine screen. While extensive efforts are made to ensure confidentiality of all research procedures, there is a possibility that confidentiality could be compromised to the detriment of the study participant. Although the supportive living environment of the SLH and supportive case management are not likely to cause psychiatric crisis such as suicide, homicide, or psychotic regression, these problems are always possible among the population we are investigating.

To minimize risk, participants will be informed before each research and case management interview that they may decline to answer questions with which they are uncomfortable, and they may terminate the interview at any time without penalty. Case management sessions and qualitative interviews will be audiotaped, but residents will be free to turn off the tape at any point. Audiotapes and case report forms will not contain any identifying information and will be kept in a locked cabinet. Audiotape recordings will be destroyed 5 years after completion of the study. Case management meetings and research interviews will only be conducted when there is sufficient privacy. We have extensive experience conducting interviews within criminal justice institutions and have not had any concerns about privacy. Typically, these meetings take place in "interview rooms" where attorneys meet with their incarcerated clients. We will obtain approval for these procedures from our IRB, the OHRP, and a federal Certificate of Confidentiality. We have used many similar items to those proposed here in other studies and have not experienced reports of excessive discomfort from participants. Risks that the research participants may undergo are expected to be minimal. The questions asked of participants in the study are opinions or typical counseling questions that clients are often asked as part of their treatment. Although the supportive living environment of the SLH and supportive case management are not likely to cause psychiatric crisis such as suicide, homicide, or psychotic regression, these problems are always possible among the population we are investigating. The therapist will be a licensed mental health professional trained in how to manage such issues. Voluntary or involuntary psychiatric hospitalization will be considered if clinically and legally appropriate. The therapist will work with local psychiatric emergency centers to coordinate hospitalization if necessary. [name] will supervise the therapists and be available for consultation as needed. [name] is a licensed mental health practitioner with many years of experience in psychiatric day treatment settings, and he has addressed psychiatric crises as a regular part of his work.

#### **G. Confidentiality**

All participant data will be reported on case report forms without identifying information. Similarly, all audiotape recordings will be coded with a number and no identifying information will be on them. Respondents will be reassured that all data will be kept under lock and key to assure confidentiality of the data. Only research staff will have access to the data. A federal Certificate of Confidentiality will be obtained for this project to add further safeguards to confidentiality.

All research staff will sign pledges of confidentiality and receive training on data security procedures. Because we may interview subjects in state prisons or local jails, we will obtain approval from the Office of Human Research Protection (OHRP). The study will be analyzed statistically in an aggregate manner and will not identify specific respondents. Data for tracking will be kept in a password protected database accessible only to staff.

Case report forms and audiotapes will be kept for 5 years after the study ends. At that point [name] will arrange for shredding of case report forms and erasure and destruction of audiotapes. All data will be kept locked during this time.

## **H. Informed Consent**

All participants will be required to sign an IRB approved consent form before beginning interviews. This form will include the following information: 1) participation is voluntary and refusing to participate or deciding to discontinue participation at any time is without penalty, 2) the general research purpose, 3) participation consists of completing questionnaires and interview questions, 4) questions will address issues pertaining to community support, substance use, psychiatric symptoms, and related problem areas (e.g., work, family and medical), 5) participants will be compensated \$30 for their participation in the baseline interview and \$50 for their participation in the 6-, and 12-month interviews as well as a \$5 gift card for confirming/updating their locator information at the 3-month interim contact and a \$10 gift card for confirming/updating their locator information at the 9-month interim contact, 6) all responses will be entirely confidential and no identifying information will appear in any research reports, 7) data will be presented in aggregate form, 8) the study is approved by the Public Health Institute Institutional Review Board (IRB), 9) the study is approved by the Office of Human Research Protection (OHRP), 10) the study has acquired a federal Certificate of Confidentiality, and 11) whom to contact if they wish additional information.

The 28 individuals selected for qualitative interviews at the 6-month interview will sign an additional consent form that describes the purpose and procedures for these interviews. They will be informed that the sessions will be audiotaped but stored in a locked file cabinet without any identifying information

## **I. Financial Issues**

There are no costs to participants taking part in the study. There are no costs associated with receiving MICM in the intervention condition and no cost for receiving a list of referral resources in the comparison condition. Payment to participants for their time completing research interviews is \$30 for participation in the baseline interview and \$50 for participation in the 6- and 12-month follow up interviews as well as a \$5 gift card for confirming/updating their locator information at the 3-month interim contact

and a \$15 gift card for confirming/updating their locator information at the 9-month interim contact. The 28 individuals taking part in the qualitative component will be compensated \$20. Individuals entering SLHs will be required to pay ordinary fees associated with living in the facility.

**Reducing Offenders' HIV Risk: MI Enhanced Case Management With Drug-Free Housing
Data Plan, Version October 7, 2016
Clinicaltrials.gov ID: NCT01977092**

Analysis

Univariate and bivariate analyses of all variables will inform development of longitudinal models to follow. These analyses will include identification of outliers and data distributions that indicate need for data transformation procedures or categorization of variables. These procedures will be important to avoid use of covariate variables that would trigger common violations of modeling assumptions. Bivariate analyses will include histograms, scatterplots, correlation matrices, χ^2 tables and ANCOVA models for all study variables. Multiple testing procedures (e.g., Bonferroni) will be used, when appropriate, to prevent inflation of type I error rates.

Longitudinal Analysis of Outcome Measures

$\alpha_{i,h} = \vartheta_{0,h} + \vartheta_1 X_{i,h} + u_{0,i,h}$ and the random slope will be parameterized as $\beta_{i,h} = \lambda_{0,h} + \lambda_1 X_{i,h} + u_{1,i,h}$ where $X_{i,h}$ are time invariant individual-level covariates (e.g., baseline age, ethnicity) and the $u_{0,h}$ and $u_{1,h}$ are random variables that indicate unexplained variation in the random intercept and slope across individuals. To assess variability of the dependent variable across houses, both at baseline (the intercept) and over time (the slope), the random intercept of the level 1 intercept ($\theta_{0,h}$) and the random intercept of the level 1 slope ($\lambda_{0,h}$) will be parameterized as

$\vartheta_{0,h} = \gamma_{0,0} + \gamma_{0,0}Z_h + v_{0,h}$ and $\lambda_{0,h} = \gamma_{1,0} + \gamma_{1,0}Z_h + v_{1,h}$ where the Z_h are house-level variables and the $v_{0,h}$ and $v_{1,h}$ are random variables indicating unexplained variation in the average growth parameters across houses. Therefore, both individual-level and house-level variables will be incorporated into the longitudinal model to predict variability in growth parameters. In

addition to accounting for the nesting of individuals within time, the models will account for the nesting of individuals within houses which, when left unconsidered even if no house level variables Z are entered into the model, may result in underestimates of level 2 model variances u_o and u_i and therefore invalid inferences for the effects of individual-level variables on longitudinal trajectories.

Dose-Response Analysis for MMI

For participants in the MMI condition we will conduct a dose-response analysis. Our rationale draws on the case management study by Longshore et al (2005). They reported a significant relationship between the number of case management contacts with residents and primary outcome variables. We will complete a similar analysis using bivariate associations (e.g., by examining χ^2 tests and estimated correlations) and multivariate models that assess dose effects controlling for selected variables.

Analysis of Specific Aims

Aim 1: *To assess HIV testing rates, HIV risk behaviors, and utilization for HIV services at baseline, 6, and 12 months.*

H1.1 Residents receiving MMI in addition to drug free housing will have higher rates of HIV testing, higher utilization of HIV services, and fewer HIV risk behaviors than the drug free housing and resource manual condition.

Hypotheses H1.1 will be tested in the framework of longitudinal models, as described above. The focus is on treatment condition which, although uniquely assigned to individuals, is implemented at the house level and therefore will be treated as a level 3 variable. This allows for a limited exploratory examination of potential treatment effects with house level characteristics. Interactions of treatment condition with level 2 variables (e.g., gender) can be implemented by simply including treatment as a predictor of the non-randomly varying level 2 coefficient (e.g., gender) of interest. Evidence in favor of the hypotheses will be significant level-3 coefficients (the relevant γ coefficient) for the indicator variables (Z) representing average differences between houses in the rate of change in the outcome over time (i.e., the intercept of the level 2 slope parameter $\lambda_{o,h}$).

Aim 2: *To compare baseline substance use within each study condition with 6- and 12-month substance use.*

H2.1 Residents in each study condition will show significant reductions in drug and alcohol use between baseline and follow-up time points as measured by the Time Line Follow Back (TLFB).

H2.2 Residents in each study condition will show significant reductions in drug and alcohol problems between baseline and follow-up time points as measured by the Addiction Severity Index alcohol and drug scales.

Hypotheses H2.1 and H2.2 will be tested in the framework of longitudinal models, as described above. As a first step, an empty model will be estimated (random intercept and slope but no level 2 (individual) or level 3 (house) covariates) to test whether the variances of the intercept and slope parameters (u and v) are significant. Should significant variation be found, candidate covariates, both at the individual level (level 2) and the house level (level 3), will be considered in separate models and any such covariates will be entered as predictors of both the random intercept and slope.

Aim 3: *To compare outcomes between the two study conditions at baseline, 6, and 12 months.*

H3.1 Residents receiving MMI in addition to drug free housing will have less substance use (TLFB) and lower ASI alcohol and drug severity than the drug free housing and resources condition.

H3.2 Residents receiving MMI in addition to drug free housing will have fewer arrests, fewer days incarcerated and lower ASI legal severity than the drug free housing and resources condition.

H3.3 Residents receiving MMI in addition to drug free housing will have fewer work problems (ASI Employment scale) and more days worked than the drug free housing and resources condition.

Testing of hypotheses in H3.1 to H3.3 will first be carried out using the same growth curve modeling methods as described for analyses proposed in Aim 1 above.

Aim 4: To assess mediators and moderators of the MMI.

H4.1 Service utilization (Hser et al., 1991) will mediate the relationship between treatment type (drug free housing with vs. without MMI) and outcome (TLFB, ASI Alcohol and Drug scales and criminal justice recidivism).

The best fitting model found from analyses in Aim 2 which include level 3 indicators of treatment condition as predictors of the average random slope (and potentially the random intercept) will serve as the baseline model with which to assess mediation. For treatment predictors of the random slope, overall significance of the 1 degree of freedom test of differences in changes over time between the 32 houses will be assessed using a linear contrast test. Then, time varying covariates (e.g., utilization of services, perceived stress, and negative affect scales) will be entered separately into the model as a level 1 (time within individual) predictor. Then, the same linear contrast test of the level 3 treatment coefficients for the random slope coefficients indicating average differences in change over time between treatment conditions will again be carried out, with reductions in the magnitude of the coefficient estimate and significance of the test indicating the degree to which such variables mediate program differences.

Exploratory Aims:

We will explore a variety of additional outcomes within and between study conditions for which we do not have a priori hypotheses. These will include additional ASI scales (Family, Medical, and Psychiatric) and Housing Status. We will also explore how a variety of covariates are associated with outcome within and across study conditions. Variables assessed will include social support, supportive confrontation, motivation, drug use, age of onset for alcohol and drug use, criminal justice history and status (probation or parole) and gang affiliation. Analytic methods will include first examining univariate distributions and bivariate associations and then entering variables as covariates into the growth curve modeling described above.

A second exploratory aim is to conduct 30 qualitative interviews (15 in each condition) to identify general and intervention specific factors that were perceived to affect outcomes and ways to improve the two active interventions. An initial coding list will include specific codes suggested by characteristics of the intervention. For example, codes for the SLH alone condition might include things like “helped me increase support to not use alcohol or drugs,” and “helped me avoid exposure to alcohol and drugs.” For MMI, codes might include “made suggestions for services” and “helped me prepare for living at the SLH.” For meditation, codes might include things like “helped me relax” and “increased positive feelings about myself.” Using line-by-line coding, themes and excerpts of text will be highlighted as quotations that exemplify salient resident attitudes and beliefs. Excerpts will be printed out, and each analyst will group the excerpts into thematic categories. The extent of agreement between the analysts’ initial coding of the data will be assessed. Each analyst will define the working themes and through discussion select a final set. Data will be entered into the qualitative software program, N Vivo. The research team will use the constant comparison method and analytic memoing to identify patterns, create themes or categories, and develop theoretical insights (Strauss & Corbin, 1990).

Power Considerations

Given our sample of 165 in each of the 2 study conditions and our expectation that we will contact 80% of the sample at 12 months we should have 132 per group and a total N of 264 available for analysis for at least two time points. For tests of equality of paired differences in means for outcomes between the final interview and baseline between the two study conditions, power to detect small-to-medium effect sizes ($d=.35$) would be .82 in 2-sided tests with $\alpha=.05$.

Similar power is available for tests of equality of proportions (Cohen, 1988).

For estimation of power in growth curve modeling, programs for estimating power are available (Bosker, 1999), but they typically require population parameters, including between- and within-subjects covariance matrices and estimates of level 1 and 2 residual variances. Other methods have been developed for testing specific slope differences (Jung & Ahn, 2005), but point estimates are still required for the variances of the slope parameter within each group for which prior information, and even ranges of plausible values, are simply not available. Instead of assuming knowledge of such population parameters, power is approximated here in the

Min N for Power=.8 in Longitudinal Models with Continuous Outcomes					
		Δ (%)			
		.2	.3	.4	.5
δ	.2	146	65	37	24
	.5	208	93	52	34
	.8	270	120	68	44

context of longitudinal Generalized Estimating Equations (GEE) models (Diggle, et al., 2002) using the attrition adjusted effective sample sizes. Various possible error variance structures in GEE models can approximate the partitioning of variance explicit in multilevel models and also provide a simpler context in which to approximate power for between groups longitudinal effects as it instead

relies only on an effect size defined in standardized units as $\Delta = d/\sigma$, where d effect size (here, the time averaged difference in the outcome variable between the two comparison groups) and σ is the unknown level 1 error variance. Assuming $\alpha=.05$ and $n=3$ interviews per respondent, the minimum sample sizes required to detect standardized effect size differences of $\Delta=(.2, .3, .4, .5)$ for exchangeable error correlation values of $\delta=(.2, .5, \text{ and } .8)$ with power of .80 are shown in the table above. Power for estimation of individual level effects associated with the first two levels comprising interviews nested within individuals uses a design effect adjusted sample size accounting for within-house correlation of responses. Assuming a medium Intraclass Correlation Coefficient of .06 (Kirk, 1995) reduces the effective attrition adjusted number of respondents from 132 to $n=132/(1+32*.06)=45$ cases. From the table, power would be close to .80 to detect small-to-medium effect size differences ($\Delta=.35$, as defined in (Cohen, 1988) in the time averaged differences between the two treatment groups when the error correlation over time is relatively moderate ($\delta = .2$). Power for estimation of level 3 coefficients is approximated in the context of simple linear regression with $n=32$ cases (houses) available. Power to detect medium to large effect size relationships ($f^2=.25$) (Cohen, 1988) between house level characteristics and time averaged differences in outcomes between the two treatment conditions would be .81.

The meta-analysis on MI outcome by Hettema et al. (2005) found pairwise between group effect sizes to be .77 (very large) in the short term and .30 at (small-to-medium) one year follow up. Therefore, power should be more than adequate.

Management Plan

The management plan is based on procedures from our recent study of SLHs (i.e., [name] et al., 2010) as well as previous multisite studies where [name] served as key personnel (Carroll et al., 2006). Coordination will be achieved using weekly telephone conference calls involving all staff on the research team. [name] and [name] will travel to Los Angeles at least quarterly for day long face to face meetings with fieldwork staff and therapists. Study therapists will be hired by [name] who will train them together (16 hours face to face) and meet with them via telephone conferencing weekly to discuss all aspects of MICM.

Timeline

Months 1-4	Recruit and train therapists and interviewers, IRB approval, Federal Certificate of Confidentiality, Review instruments and data collection procedures, Complete Procedures Manual and Question-by-Question guidelines, Pilot test interventions and data collection procedures.
Months 5-43	Recruit approximately 8 study participants per month over 38 months. Finish data cleaning for baseline data at month 43.
Months 44-52	Complete all follow up interviews.
Months 53-60	Complete longitudinal analysis of data. Submit papers to addiction and criminal justice journals as well as trade magazines for addiction professionals. Present final analyses to consumers and other stakeholders.

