### **Structure of MICM Sessions**

Participants assigned to the MICM condition will receive 3 individual sessions within the first month of entering the SLH. Thereafter they will have contact with the MICM therapist monthly throughout the duration of their enrollment in the study (12 months). However, therapists will also be available to address crises that occur, such as

psychiatric emergencies, arrests, and sudden loss of job or housing. For participants who have left the geographical area the session will be conducted by phone.

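### The dose-response analysis does not define dose, separate crisis contacts from scheduled ones, or place dose before outcome, so a simple contact count would be partly caused by arrests and by loss of job or housing.

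*SAP*

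**What the plan says.** The SAP, under Dose-Response Analysis for MMI (read here as the protocol's MICM), states: "For participants in the MMI condition we will conduct a dose-response analysis". Its rationale is a cited case management study, which is said to have found a "significant relationship between the number of case management contacts with residents and primary outcome variables". The method follows that study: "We will complete a similar analysis using bivariate associations", with chi-square tests and correlations as examples, and then "multivariate models that assess dose effects controlling for selected variables". The control variables are not named. The section gives no definition of dose, no time window and no limit on interpretation.

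The protocol, under Structure of MICM Sessions, sets a fixed schedule: participants "will receive 3 individual sessions within the first month of entering the SLH" and then have monthly contact to month 12. It continues: "However, therapists will also be available to address crises that occur", and gives as examples "psychiatric emergencies, arrests, and sudden loss of job or housing".

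Under Primary Outcomes the protocol lists violations, arrests and days incarcerated, among others. Under Secondary Outcomes it lists days worked and housing stability.

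**The concern.** Some of the events that can generate a therapist contact are also trial outcomes. If dose is simply the number of contacts, an arrest can add to both sides of the association. That is reverse causation. Adjusting for baseline characteristics cannot remove it, because the dose is partly recorded after the outcome and in response to it.

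The opposite bias is also plausible. A participant who is arrested or incarcerated may miss monthly sessions, so fewer contacts would go with worse outcomes even if contacts did nothing.

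The analysis could therefore suggest that more MICM does harm, or does good, when dose has no effect. The SAP speaks of dose effects on primary outcomes and gives no caution on how to read them.

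**Working it through.** **Plan's own figure.** The documents give no sample size, power or effect size for this analysis, so there is nothing to reproduce. What follows is an illustration with the true dose effect set to zero.

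**Inputs from the documents**
- Participants analysed: 165 × 0.80 = 132 in the intervention arm (SAP, Power Considerations).
- Scheduled contacts: 3 in month 1 plus 11 monthly = 14 (protocol, Structure of MICM Sessions).
- Arrests: 37% of probationers and parolees rearrested by 6 months in the preliminary study (protocol, section A). If arrests are Poisson, the 12-month mean is λ = −2 ln(1 − 0.37) = 0.924.
- Two-sided α = 0.05, as in the SAP's power section.

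**Assumptions not in the documents**
- Attendance at scheduled contacts is 70%.
- A fraction q of arrests each adds one crisis contact.
- Each arrest removes on average m scheduled contacts.

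**Crisis contacts only (m = 0), same attendance probability for everyone.** The covariance of contacts with arrests is qλ. The variance of contacts is 14 × 0.7 × 0.3 + qλ = 2.94 + qλ. So

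r = qλ / √[λ(2.94 + qλ)],

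and the chance of a significant harm signal is about Φ(atanh(r)·√129 − 1.96).

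- q = 0.10: r = 0.0924 / √(0.924 × 3.032) = 0.055; Φ(0.63 − 1.96) = 9%.
- q = 0.25: r = 0.231 / √(0.924 × 3.171) = 0.135; Φ(1.54 − 1.96) = 34%.
- q = 0.50: r = 0.462 / √(0.924 × 3.402) = 0.26; Φ(3.03 − 1.96) = 86%.
- q = 1: r = 0.924 / √(0.924 × 3.864) = 0.49; about 100%.

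A simulation of 4,000 arms gave the same 34%, 86% and 100% for q = 0.25, 0.50 and 1. The chance rate in this direction is about 2.5%.

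**Sensitivity to attendance and arrest distribution.** If attendance varies between participants, the extra spread in contacts dilutes the correlation. Re-simulation under alternative assumptions gave these false harm rates:

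| Share of arrests adding a contact | Same attendance, Poisson arrests | Alternative assumptions |
|---|---|---|
| 10% | 9% | about 6–7% |
| 25% | 34% | 14–24% |
| 50% | 86% | 44–68% |
| 100% | 100% | 93–100% |

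**Missed sessions only (q = 0), same attendance.** The covariance is −0.7mλ. For m = 1 the variance of contacts is 0.21 × (14 − 0.924) + 0.49 × (2 × 0.924) = 3.65, so r = −0.647 / √(0.924 × 3.65) = −0.35. The simulation gave a false benefit signal in 98% of runs. For m = 2 it gave r = −0.58 and 100%. Counting scheduled contacts alone does not remove this bias, since these contacts are the ones lost.

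**Both together.** The covariance is λ(q − 0.7m). It is zero when an arrest costs as many attended contacts as it adds. With q = 0.5, this is 0.5 attended contacts, or 0.5 / 0.7 = 0.71 scheduled ones. Away from that point the sign can go either way: q = 1 with m = 1 gave r = +0.16, and q = 0.25 with m = 2 gave r = −0.49.

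**Check of the fix.** Scheduled contacts to month 6 were related to arrests in months 6 to 12, adjusted for arrests by month 6. False positives were about 4–6% in every scenario, including both mechanisms together. This check assumes that attendance is otherwise unrelated to arrest risk.

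**The case against.** A reader might infer that the SAP counts every therapist contact, and does so over the same period as the outcomes. The documents do not say either. The words on number of contacts describe the cited study; for this trial the SAP promises only a similar analysis and sets no window, concurrent or lagged. The supportable point is that dose and timing are undefined, although an unrestricted contact count is the natural reading.

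A reader might also extend the bias to all primary outcomes. Substance use and HIV risk are not among the named crisis triggers, so they are less directly affected. The figures above concern arrests, the outcome most closely tied to the trigger.

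The missed-session mechanism is partly mitigated. The protocol provides phone sessions for participants who leave the area, and Assessment of Risks describes private meetings in criminal justice institutions. The number of sessions lost per arrest is not given.

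The percentages depend on chosen inputs. At a low trigger rate the distortion is small, and the two mechanisms can cancel. That stands, so no single percentage should be quoted as the size of the problem.

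Finally, the analysis covers one arm, belongs to no numbered hypothesis, and nothing says it will set how much MICM to deliver. That limits the weight of the point. It does not remove the point, because the SAP gives the analysis its own section and aims it at primary outcomes.

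**Conclusion.** The concern holds in a limited form. The SAP leaves dose undefined, does not separate scheduled from crisis-triggered contacts and sets no time order, while the protocol lets arrests and loss of job or housing generate contacts. A plain contact count is then partly a consequence of those outcomes, and nothing in either document corrects for it.

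The existence and direction of each bias follow from the design: added crisis contacts point towards harm, missed sessions towards benefit. The size and net sign do not. With no true effect and n = 132, false harm signals run from about 6–9% if 10% of arrests add a contact to over 90% if all do, and a false benefit is possible if missed sessions dominate. These figures rest on assumed attendance, trigger rates and lost sessions.

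The change should be made before any dose result is reported. It is not critical to the trial, because the randomised comparisons are unaffected.

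**What to change.** Amend the SAP section to:
- define dose as scheduled MICM contacts completed by the 6-month interview;
- report crisis-triggered contacts separately, by reason;
- relate dose to outcomes in the 6-to-12-month window, adjusting for baseline severity and the 6-month value of the outcome, and name the other control variables;
- label the result observational, because participants who attend more may differ in ways the adjustment does not capture.

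The cost is a few sentences in the SAP and a scheduled-or-crisis flag for each contact in the therapist log. First-half outcomes serve only as adjustment variables in this analysis. As the protocol's Measures table reads, work history is collected at baseline and one year only. For days worked, the 6-month adjustment could use the ASI employment scale, which the table shows at all three interviews. No clinical procedure changes.
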